14.2.1.10.1 Swimmer Plot (All-Treated Population)

14.2.1.10.2 Swimmer Plot (Per-Protocol Population)

14.2.1.11.1 Kaplan-Meier Plot of Time to First AE Leading to Dose Modification (All-Treated Population)

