Dose-limiting toxicity was reported in 3 patients (2 thrombocytopenia and 1 febrile neutropenia).

Serious adverse events (SAEs) were reported in 54 (37.5%) out of 144 patients. Of these, 24 patients experienced an SAE(s) considered at least possibly related to study drug. Six of the possibly related events were observed in multiple patients (febrile neutropenia in 5 patients, pyrexia in 3 patients, dyspnea in 2 patients, lung infection in 2 patients, pleural effusion in 2 patients, and sepsis in 2 patients). Preliminary data indicate an acceptable safety profile. Febrile neutropenia and pleural effusion have been classified as expected serious ADRs.

Out of 126 evaluable patients, 33 (26.2%) achieved CR and 25 (19.8%) achieved PR, for an ORR of 58/126 (46.0%).

Out of 92 evaluable patients with DLBCL, 22 (23.9%) achieved CR and 16 (17.4%) achieved PR, for an ORR of 38/92 (41.3%).

Additional details may be found in the current loncastuximab tesirine Investigator's Brochure (IB).

2 Study Rationale

Human CD19 antigen is a 95 kd transmembrane glycoprotein belonging to the immunoglobulin superfamily. In normal human tissue, expression of CD19 continues through pre-B and mature B-cell differentiation until it is finally down-regulated during terminal differentiation into plasma cells (Scheuermann, 1995); however, expression of CD19 is maintained in hematologic B-cell malignancies, including DLBCL.

Loncastuximab tesirine is an ADC that has been designed to target and kill CD19-expressing malignant B-cells. Preliminary data from a Phase 1 study of loncastuximab tesirine in relapsed or refractory B-cell NHL (Section 1.3) shows significant activity of loncastuximab tesirine with an acceptable safety profile in patients with DLBCL.

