4.3 Treatment Period

The treatment period starts on the date when a patient receives the first dose of study drug and continues until the date of discontinuation from treatment.

A treatment cycle is defined as 3 weeks (i.e., 21 days). Loncastuximab tesirine will be administered as an intravenous (IV) infusion over 30 minutes on Day 1 of each cycle. Patients will receive 150 $\mu\text{g}/\text{kg}$ Q3W for 2 cycles, then 75 $\mu\text{g}/\text{kg}$ Q3W for subsequent cycles.

Patients may continue treatment for up to one year or until disease progression, unacceptable toxicity, or other discontinuation criteria ([Section 7](#)), whichever occurs first. Additionally, patients benefitting clinically at 1 year may continue treatment after a case by case review with the Sponsor.

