9.1 Sample Size Calculation

Patients with DLBCL who have failed second line therapy have a very poor prognosis, with response to second-line salvage therapy ranging from 14-26%, with a median survival of 6.1 months (Seshadri et al., 2008; Crump et al., 2017). A treatment with a response rate of 20% would be a clinically meaningful option for this patient population.

The primary hypothesis is that the ORR based on central review for patients treated with loncastuximab tesirine is significantly greater than 20% (i.e., $H_0: p \leq 0.2$ vs. $H_a: p > 0.2$). This hypothesis will be tested at type I error of 0.05 (two sided).

Using nQuery exact test for single proportion, a sample size of 140 patients has >99% power to achieve a 1-sided significance level of 0.025 (2-sided significance level of 0.05). This sample size will provide adequate precision for observed ORR in the expected range. A 2-stage design will be used, with an interim analysis for futility on the first 52 patients. If ≥ 10 patients respond, the study will proceed to complete full enrollment. Enrollment will continue during the interim analysis; however, further enrollment will be halted if futility is confirmed to minimize exposure of patients in the study. With the null hypothesis that the true response rate is 0.2, and the alternative hypothesis that the true response rate is significantly greater than 20%, (40% is used for calculation), the design controls the type I error rate at 0.025 and yields a power of >99%.

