3.3 Modifications to the statistical section of the protocol

NA.

4 Statistical methods

All analyses use SAS[®] version 9.4 or higher. All available data will be used in the analyses, and important data will be included in data listings, sorted by patient, and by visit within patient. Missing data will not be imputed, except via censoring in survival analyses and as otherwise specified.

Unless otherwise noted, categorical data will be presented using counts and percentages, with the number of patients in the analysis population as the denominator for percentages. Percentages will be rounded to one decimal place, except 100% will be displayed without any decimal places and percentages will not be displayed for zero counts. Continuous data, unless otherwise noted, will be summarized using the number of observations (n), mean, standard deviation (std), median, minimum, and maximum. Minima and maxima will be rounded to the precision of the original value, and means, medians, and 95% confidence intervals (CIs) if presented will be rounded to 1 decimal place greater than the precision of the original value. The std will be rounded to 2 decimal places greater than the precision of the original value, up to a maximum of 3 decimal places.

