4.8.1 Adverse Events, Serious Adverse Events, and Deaths

4.8.1.1 Analyses of adverse events

The primary focus of adverse event reporting will be on TEAEs. An adverse event (AE) will be considered to be a TEAE if it begins or worsens on or after the first dose date and until 30 days after the last dose date, or start of a new anticancer therapy/procedure, whichever comes earlier.

An AE occurring before the first dose or more than 30 days after the last dose date or after the start of a new anticancer therapy/procedure will not be included in TEAE displays, but will be listed as non-TEAEs.

If an AE date/time of onset (occurrence, worsening, or becoming serious) is incomplete, an imputation algorithm will be used to classify the AE as pre-treatment, TEAE, or post-treatment. The algorithm for imputing date/time of onset will be conservative and will classify an AE as treatment-emergent unless there is definitive information to determine it is a non-TEAE (pre- or post-treatment). Some details on classification of AEs with missing or partial onset dates are provided in Section 7.

Analysis of all TEAE(s):

The following TEAE summaries will be generated for the all-treatment population.

- Overview of TEAEs, summarizing number of TEAE and number (%) of patients with any
 - TEAE
 - Related TEAE (including possibly related, probably related, or related)

- Any TEAE \geq Grade 3
- Serious TEAE
- TEAE leading to death
- TEAE leading to permanent treatment withdrawal
- TEAE leading to loncastuximab tesirine delay or reduction or interruption (if applicable)
- TEAE with at least one infusion related reaction
- All TEAEs \geq Grade 3 by PT, showing number (%) of patients with at least one TEAE, sorted by decreasing incidence of PTs
- All TEAEs by primary System Organ Class (SOC) and PT, showing number (%) of patients with at least one TEAE, sorted by SOC in alphabetic agreed order and decreasing incidence of PTs within SOC. This sorting order will be applied to all other tables, unless otherwise specified.
- All TEAEs by primary SOC, PT and Maximal CTCAE grade, showing number (%) of patients with at least one TEAE, sorted by SOC and PT in alphabetic order. This sorting order will be applied to all other tables, unless otherwise specified.
- All TEAEs \geq Grade 3 by primary SOC, PT and Maximal CTCAE grade
- All related TEAEs by primary SOC, PT and Maximal CTCAE grade (including possibly related, probably related, or related)

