Appendix 2 List of Post-Text Tables, Figures, Listings, and Supportive SAS Output Appendices

This list of outputs is for the purpose of programming instruction, the SAP is not required to be updated for changes in future list.

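### The planned Kaplan-Meier curve for AE-driven dose modification has no event, censoring or competing-event rule; if patients who leave treatment for other reasons are censored, it overstates the share of treated patients modified

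*SAP*

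**What the plan says.** The figure appears only as a title, 14.2.1.11.1, among the efficacy figures in SAP Appendix 2: "Kaplan-Meier Plot of Time to First AE Leading to Dose Modification (All-Treated Population". The appendix introduces itself with "This list of outputs is for the purpose of programming instruction" and adds that the SAP need not be updated when the list changes.

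The SAP body gives this figure no event definition, time origin, censoring rule or competing-event rule. The other time-to-event outcomes have written censoring rules (SAP 4.9.2 and 4.9.5 to 4.9.7). The only general statement that could apply is in SAP section 4: "Missing data will not be imputed, except via censoring in survival analyses and as otherwise specified".

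Two other provisions bear on the point. Protocol 4.3 states: "Patients may continue treatment for up to one year or until disease progression, unacceptable toxicity, or other discontinuation criteria". SAP 4.8.1.1 counts an adverse event as treatment-emergent only "until 30 days after the last dose date, or start of a new anticancer therapy/procedure, whichever comes earlier".

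The same SAP section also plans crude numbers and percentages of treated patients with treatment-emergent events that led to delay, reduction, interruption or withdrawal.

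**The concern.** Once a patient has stopped the drug for progression, death or personal decision, there is no dose left to modify. That is a competing event, not incomplete follow-up. Kaplan-Meier with these patients censored treats them as still able to have the event. It then estimates the risk of modification if nobody left treatment for another reason, and does so only if leaving is independent of the risk of toxicity.

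The figure is labelled for all treated patients, so it is likely to be read as the share of them who needed a modification. Read that way, it overstates the burden of dose modification. The study report would also carry two tolerability figures that disagree, the curve and the crude tables, with nothing to explain the gap.

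**Working it through.** The plan states no number for this figure, so there is none to reproduce. The documents give no dose-modification rate, no time on treatment and no split of reasons for stopping. The calculation therefore rests on assumed hazards.

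**Inputs from the documents**
- Historical survival in comparable patients: "with a median survival of 6.1 months" (Protocol 9.1).
- Phase 1 (Protocol 1.3): 38 of 92 DLBCL patients responded (41.3%), so 58.7% did not. Treatment-emergent events led 16 of 144 patients (11.1%) to discontinue.

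These make non-AE exits plausible but do not fix their rate.

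**Model.** Two independent constant hazards: l1 for the first AE-driven modification, l2 for leaving treatment first for a non-AE reason.
- Kaplan-Meier with leavers censored: 1 − KM(t) = 1 − exp(−l1·t)
- Cumulative incidence: CIF(t) = l1/(l1 + l2) × [1 − exp(−(l1 + l2)·t)]

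**Worked line.** Suppose 1 − KM is 50% at Week 24 and the median exit time is 12 weeks. Then l1 = ln 2/24 = 0.02888 per week, l2 = ln 2/12 = 0.05776, and the sum is 0.08664. CIF = 0.3333 × [1 − exp(−2.079)] = 0.3333 × 0.875 = 29.2%. The ratio is 50/29.2 = 1.7.

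**Week 24 results**

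| Assumed median exit | CIF when 1 − KM = 50% | Ratio | CIF when 1 − KM = 70% | Ratio |
|---|---|---|---|---|
| 6 weeks | 19.4% | 2.6 | 29.7% | 2.4 |
| 9 weeks | 25.1% | 2.0 | 37.6% | 1.9 |
| 12 weeks | 29.2% | 1.7 | 43.0% | 1.6 |
| 18 weeks | 34.4% | 1.5 | 49.8% | 1.4 |
| 6.1 months (about 26.5 weeks), death alone | 38% | 1.3 | 55% | 1.3 |

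The last row uses the only competing-event time in the documents. It leaves out progression and every other exit.

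**At 12 months, for a true incidence of 10% to 50%**
- Median exit of 3 months: factor 1.88 to 2.77.
- Median exit of 12 months: factor 1.31 to 1.37.
- Death alone at 6.1 months: factor 1.57 to 1.79.

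**Early toxicity.** Let l1 be 0.25 to 0.30 per month for the first 1.4 months (about two cycles) and 0.02 to 0.15 afterwards. With a median exit of 3 to 4 months, the factor at 12 months falls to 1.37 to 1.80. For example, 0.30 then 0.05 gives 1 − KM = 1 − exp(−(0.30×1.4 + 0.05×10.6)) = 61.3%, against a simulated incidence of 37.6% at a 3-month median exit: factor 1.63.

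**Censoring rule.** In a simulation of 200,000 patients with l1 = 0.10 per month and a 3-month median exit, 29.6% were modified by 12 months and the censored Kaplan-Meier estimate was 69.7%. When leavers were kept in the risk set to the end of the period, the estimate was 29.6% and the bias vanished.

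**The case against.** The strongest case against the point has four parts.

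1. **The censoring rule is unwritten.** If leavers stay at risk until the data cut, there is no bias. That is correct, and the point is conditional on it. But the general reference to censoring and the closing of the adverse event window after the last dose make censoring at or near treatment end the natural default. The missing rule is itself something to settle.

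2. **Kaplan-Meier with leavers censored answers a legitimate question.** That question is the risk while treatment continues, under independent censoring. This stands. The curve misleads only if read as the proportion of treated patients modified, and the figure carries nothing to prevent that reading.

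3. **The crude share is already planned.** SAP 4.8.1.1 gives it in tables. This limits the harm. It does not make the curve an estimate of the same quantity.

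4. **The consequence is small.** The safety analyses are descriptive, and no endpoint or decision uses the figure. This also stands.

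A reader might go further and infer that most patients will leave for progression or death before any modification. The documents do not say so. Protocol 4.3 lists reasons for ending treatment without frequencies or order, and the 6.1 months is historical survival, not time on this drug. Other passages point towards early modification: Phase 1 reported Grade 3 or higher treatment-emergent events in 63.9% of patients, and Protocol 6.4 requires the drug to be held for a range of toxicities.

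A reader might also infer that the curve will be about double the truth. That is one point in an assumed range. At Week 24 it needs a median exit near 9 weeks or shorter, and a 6-week median means half the patients are gone by the first on-treatment scan (Protocol 8.1).

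**Conclusion.** The concern holds in conditional form. A Kaplan-Meier curve is planned for an event that leaving treatment precludes, and no event, censoring or competing-event rule is given. If leavers are censored, one minus the curve exceeds the proportion of treated patients modified.

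The documents do not determine by how much. The Week 24 factors of about 1.4 to 2.6, and of about 1.3 with death alone competing, assume independent, constant hazards. Early-clustering toxicity would reduce the excess, and another censoring rule could remove it. Severity is low: this is one descriptive figure with crude percentages tabulated elsewhere.

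**What to change.** Replace figure 14.2.1.11.1 with an Aalen-Johansen cumulative incidence plot in the all-treated population, measured from first dose. Treat death and discontinuation for non-AE reasons as competing events, censor patients still on treatment at the data cut, and report the incidence with 95% CI at fixed weeks.

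State which AE-driven actions count as the event: delay, reduction, interruption, withdrawal. This needs an explicit choice, because Protocol 9.7.1 lists modification separately from interruption and discontinuation. If AE-driven withdrawal is not counted as an event, it also has to be a competing event, since it too rules out a later modification. If the Kaplan-Meier curve is kept as well, label it as the risk while treatment continues.

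The cost is one figure to reprogram and a short event definition. Protocol section 7 already has discontinuation reasons and dates collected for all patients, so no new data are needed.

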14.3 SAFETY FIGURES

14.3.4.1.1.1 Mean (SE) Plot of Basophils ($10^9/L$) by Dose Group (All-Treated Population)

14.3.4.1.1.2 Mean (SE) Plot of Eosinophils ($10^9/L$) by Dose Group (All-Treated Population)

14.3.4.1.1.3 Mean (SE) Plot of Hematocrit (fraction of 1) by Dose Group (All-Treated Population)

14.3.4.1.1.4 Mean (SE) Plot of Hemoglobin (g/L) by Dose Group (All-Treated Population)

14.3.4.1.1.5 Mean (SE) Plot of Lymphocytes ($10^9/L$) by Dose Group (All-Treated Population)

14.3.4.1.1.6 Mean (SE) Plot of Monocytes ($10^9/L$) by Dose Group (All-Treated Population)

14.3.4.1.1.7 Mean (SE) Plot of Neutrophils ($10^9/L$) by Dose Group (All-Treated Population)

14.3.4.1.1.8 Mean (SE) Plot of Platelets ($10^9/L$) by Dose Group (All-Treated Population)

14.3.4.1.1.9 Mean (SE) Plot of Leukocytes ($10^9/L$) by Dose Group (All-Treated Population)

14.3.4.1.1.10 Mean (SE) Plot of Basophils/Leukocytes (fraction of 1) by Dose Group (All-Treated Population)

14.3.4.1.1.11 Mean (SE) Plot of Eosinophils/Leukocytes (fraction of 1) by Dose Group (All-Treated Population)

14.3.4.1.1.12 Mean (SE) Plot of Lymphocytes/Leukocytes (fraction of 1) by Dose Group (All-Treated Population)

14.3.4.1.1.13 Mean (SE) Plot of Monocytes/Leukocytes (fraction of 1) by Dose Group (All-Treated Population)

14.3.4.1.1.14 Mean (SE) Plot of Neutrophils/Leukocytes (fraction of 1) by Dose Group (All-Treated Population)

14.3.4.2.1.1 Mean (SE) Plot of Albumin (g/L) by Dose Group (All-Treated Population)

14.3.4.2.1.2 Mean (SE) Plot of Alanine Aminotransferase (U/L) by Dose Group (All-Treated Population)

14.3.4.2.1.3 Mean (SE) Plot of Aspartate Aminotransferase (U/L) by Dose Group (All-Treated Population)

14.3.4.2.1.4 Mean (SE) Plot of Alkaline Phosphatase (U/L) by Dose Group (All-Treated Population)

14.3.4.2.1.5 Mean (SE) Plot of Bilirubin ($\mu\text{mol/L}$) by Dose Group (All-Treated Population)

14.3.4.2.1.6 Mean (SE) Plot of Gamma Glutamyl Transferase (U/L) by Dose Group (All-Treated Population)

14.3.4.2.1.7 Mean (SE) Plot of Amylase (U/L) by Dose Group (All-Treated Population)

14.3.4.2.1.8 Mean (SE) Plot of Bicarbonate (mmol/L) by Dose Group (All-Treated Population)

14.3.4.2.1.9 Mean (SE) Plot of Blood Urea Nitrogen (mmol/L) by Dose Group (All-Treated Population)

14.3.4.2.1.10 Mean (SE) Plot of Calcium (mmol/L) by Dose Group (All-Treated Population)

14.3.4.2.1.11 Mean (SE) Plot of Cholesterol (mmol/L) by Dose Group (All-Treated Population)

14.3.4.2.1.12 Mean (SE) Plot of Creatine Kinase (U/L) by Dose Group (All-Treated Population)

14.3.4.2.1.13 Mean (SE) Plot of Chloride (mmol/L) by Dose Group (All-Treated Population)

14.3.4.2.1.14 Mean (SE) Plot of Creatinine ($\mu\text{mol/L}$) by Dose Group (All-Treated Population)

14.3.4.2.1.15 Mean (SE) Plot of Creatinine Clearance (mL/min) by Dose Group (All-Treated Population)

14.3.4.2.1.16 Mean (SE) Plot of Glucose (mmol/L) by Dose Group (All-Treated Population)

14.3.4.2.1.17 Mean (SE) Plot of Potassium (mmol/L) by Dose Group (All-Treated Population)

14.3.4.2.1.18 Mean (SE) Plot of Lactate Dehydrogenase (U/L) by Dose Group (All-Treated Population)

14.3.4.2.1.19 Mean (SE) Plot of Lipase (U/L) by Dose Group (All-Treated Population)

14.3.4.2.1.20 Mean (SE) Plot of Magnesium (mmol/L) by Dose Group (All-Treated Population)

14.3.4.2.1.21 Mean (SE) Plot of Phosphate (mmol/L) by Dose Group (All-Treated Population)

14.3.4.2.1.22 Mean (SE) Plot of Protein (g/L) by Dose Group (All-Treated Population)

14.3.4.2.1.23 Mean (SE) Plot of Sodium (mmol/L) by Dose Group (All-Treated Population)

14.3.4.2.1.24 Mean (SE) Plot of Triglycerides (mmol/L) by Dose Group (All-Treated Population)

14.3.4.2.1.25 Mean (SE) Plot of Urea (mmol/L) by Dose Group (All-Treated Population)

14.3.5.1.1 Mean (SE) Plot of ECG Heart Rate (beats/min) by Dose Group (All-Treated Population)

14.3.5.1.2 Mean (SE) Plot of QTc (msec) by Dose Group (All-Treated Population)

16 LISTINGS

16.1.1 Demographic and Baseline Data (All-Treated Population)

16.1.2 Patients Disposition (All-Treated Population)

16.1.3 Number of Prior Therapies and Best Overall Response (All-Treated Population)

16.1.4 Cancer History (All-Treated Population)

16.1.5 Prior and Concomitant Medications (All-Treated Population)

16.1.6 Dosing Pre-Medication (All-Treated Population)

16.1.7 Prior Systemic Anticancer Therapy (All-Treated Population)

16.1.8 Prior Surgery (All-Treated Population)

16.1.9 Prior Radiotherapy (All-Treated Population)

16.1.10 Prior Stem Cell Transplant (All-Treated Population)

16.1.11 Medical History (All-Treated Population)

16.1.12 Subsequent Anticancer Therapy and Procedures (All-Treated Population)

16.1.13 Cytogenetic Analysis (All-Treated Population)

16.1.14 Immunophenotypic Analysis (All-Treated Population)

16.1.15 Important Protocol Deviation (All-Treated Population)

16.2.1 Tumor Measurements and Evaluations (All-Treated Population)

16.2.2 Duration of Response (DOR), Progression-free Survival (PFS), Regression-free Survival (RFS) and Overall Survival (OS) (All-Treated Population)

16.3.1 ADCT-402 Exposure and Infusion Details (All-Treated Population)

16.4.1 Adverse Events (All-Treated Population)

16.4.2.1 Treatment-emergent Serious Adverse Events (All-Treated Population)

16.4.2.2 Nontreatment-emergent Serious Adverse Events (All-Treated Population)

16.4.3 Treatment-Emergent Adverse Events Leading to Treatment Withdrawal (All-Treated Population)

16.4.4.1 Treatment-emergent Adverse Events Leading to Death (All-Treated Population)

16.4.4.2 Nontreatment-emergent Adverse Events Leading to Death (All-Treated Population)

16.4.5 Infusion Related Reaction Treatment-emergent Adverse Events (All-Treated Population)

- 16.4.6 Treatment-emergent Adverse Events Leading to Dose Reduction (All-Treated Population)
- 16.4.7 Treatment-emergent Adverse Events Leading to Dose Delay (All-Treated Population)
- 16.4.8 Treatment-emergent Adverse Events Leading to Dose Interruption (All-Treated Population)
- 16.4.9 All-cause Deaths (All-Treated Population)
- 16.4.10 Vital Signs (All-Treated Population)
- 16.4.11 Electrocardiogram Results (All-Treated Population)
- 16.4.12 Laboratory Analysis Data: Hematology (All-Treated Population)
- 16.4.13 Laboratory Analysis Data: Biochemistry Data (All-Treated Population)
- 16.4.14 Laboratory Analysis Data: Coagulation (All-Treated Population)
- 16.4.15 Laboratory Analysis Data: Urinalysis (All-Treated Population)
- 16.4.16 ECOG Performance Status (All-Treated Population)
- 16.4.17 EQ-5D-5L Individual Dimension Response and VAS Score (PRO Population)
- 16.4.18 FACT-Lym Individual Item, Subscale Scores, and Composite Scores (PRO Population)
